Detailed and descriptive analyses will be provided for all adverse events, including specific treatment required and outcomes for all secondary surgeries at the index and adjacent levels, any deaths, and all potential device related adverse events. Adverse event incidence rates, severities and time course will be determined. For subsequent surgical procedures, at every treated level, the type of surgical procedure required the incidence rate and time course will be determined and reported.

¹ Normand, S. T. (1999). Tutorial in biostatistics meta-analysis: Formulating, evaluating, combining, and reporting. *Statist. Med.* (18), 321-359.

All of the safety endpoints will be summarized descriptively at all available assessments. Summaries will be chosen as appropriate for the scale and distribution of the measures being analyzed. For categorical variables, summaries will consist of counts and percentages to describe the distribution of the endpoint. For continuous variables, descriptive summaries will consist of N, Mean, Median, Standard Deviation, Minimum and Maximum. Similarly, exact incidence and rates of AEs and subsequent surgical procedures will be calculated for the experimental group and whenever possible for the control group.

Assessing adverse events (AEs) using only the literature control data is not sufficient, because of the heterogeneity of reporting across the manuscripts. Thus, we propose using the observed data from the recent Dynesys IDE clinical study (historical). The AEs collected in this study (historical) is expected to have a similar profile as those in the present study (experimental). A test for non-inferiority will be performed using both incidence and rates, for each AE category, in both the historical control and experimental group. Non-inferiority will be inferred if the lower limit of the 95% confidence interval around the treatment difference between the 2 groups is greater than $\delta = -10\%$, using the hypotheses below where p_e is the incidence or rate in the experimental group and p_d is the incidence or rate in the historical study group.

$$H_0: p_e - p_d \leq -0.10$$
$$H_1: p_e - p_d > -0.10$$

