In addition, for each category of AE in the experimental group, a non-inferiority analysis will be performed assessing how the incidence and rates in the experimental group compare to the AEs as described in each of the contributing articles that were used for the meta-analysis. The incident rate that occurs in the experimental data will be computed with a 95% confidence interval. Any AEs that occurred in any of the literature control studies will be compared to those ranges to ensure that the incidence or rate found in the experimental group does not exceed the incidence or rate in the literature data. Non-inferiority will be inferred if the assessment of AEs under both analyses meets the specified criteria for non-inferiority.

Any explanted devices will be retrieved and evaluated for determination of failure modes and causes. Any correlation between the subject's demographic data and device failure will be determined.

D. Analysis of Additional Endpoints

Fusion status, at all time intervals other than the 24 month, as well as any other collected endpoints will be analyzed to assess the overall safety of the patient population in this investigation.

The following post-operative outcomes will be summarized:

- Neurologic Assessment
- Medication Usage
- Employment Status
- Pain Assessment
- Satisfaction Assessment
- Oswestry Disability Index (ODI)

These and any additional endpoints will be summarized descriptively at all available assessments, both as originally collected and with a change from baseline calculation including the number of subjects who improved, the number who deteriorated and the number who stayed the same from baseline. Summaries will be chosen as appropriate for the scale and distribution of the measures being analyzed. For categorical variables, summaries will consist of counts and percentages to describe the distribution of the endpoint. For continuous variables, descriptive summaries will consist of N, Mean, Median, Standard Deviation, Minimum, and Maximum.

To compare the AEs that are collected in the experimental group to the literature data, in all interim clinical summaries, as well as the final clinical summary, a tabular comparison of incidence observed for all literature reported AEs or secondary surgeries to those prospectively captured will be presented in a format similar to the table below:

Adverse Event	Article #1	Article #2	etc	522i Result
Screw Fracture				
Pseudarthrosis				
Secondary Surgery				
Revision				

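### The adverse-event non-inferiority test against the earlier IDE study runs in the wrong direction: it passes a large excess of events and fails a clearly safer device

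*Combined protocol and SAP*

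**What the plan says.** Section V.C (Primary Analysis: Safety Endpoints and Evaluation) sets up two AE comparisons.

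The first is with the earlier Dynesys IDE study: "A test for non-inferiority will be performed using both incidence and rates, for each AE category, in both the historical control and experimental group". The symbols are defined as AE frequencies. For the study device, "p_e is the incidence or rate in the experimental group"; for the IDE control, "p_d is the incidence or rate in the historical study group". The decision rule is: "Non-inferiority will be inferred if the lower limit of the 95% confidence interval around the treatment difference between the 2 groups is greater than" the margin, which is set at −10%. The hypotheses are H0: p_e − p_d ≤ −0.10 and H1: p_e − p_d > −0.10.

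The second is with the individual articles behind the meta-analysis. Its aim is that the experimental figure "does not exceed the incidence or rate in the literature data".

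The two are then joined: "Non-inferiority will be inferred if the assessment of AEs under both analyses meets the specified criteria for non-inferiority".

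Section V.G gives the fusion test in the same form: lower 95% limit above −10%, with H0: p_e − p_c ≤ −0.10.

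**The concern.** Fusion is a benefit, so a floor on the difference is the right protection. An adverse event is a harm, and the protection needed is a ceiling. V.C applies the fusion floor to AE incidence. Its null hypothesis therefore says that the study device has at least 10 points fewer events than the IDE control. Rejecting that null says nothing about how many more events the device may have.

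The study's stated purpose begins with the safety profile, and V.C is labelled a primary analysis. The IDE comparison was added because V.C regards published AE data alone as inadequate, owing to uneven reporting. A claim of non-inferior safety would thus rest partly on a test that cannot see harm. A real safety advantage could also be recorded as a failure.

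**Working it through.** **1. Direction.** The prose rule and both hypotheses in V.C agree with each other, so this is not one misprinted symbol. Nothing in Section V redefines p as an AE-free proportion or reverses the difference. Set side by side:

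| | Fusion (V.G) | AEs (V.C) |
|---|---|---|
| Higher value means | better | worse |
| H0 | p_e − p_c ≤ −0.10 | p_e − p_d ≤ −0.10 |
| H0 in words | device at least 10 points worse | device at least 10 points better |
| Pass if | lower limit > −10% | lower limit > −10% |

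**2. Rare categories.** Since p_e ≥ 0, p_e − p_d ≥ −p_d. If p_d < 0.10, the difference cannot reach −0.10, so H0 cannot be true and the test is empty. The blindness to harm is not confined to these categories; it holds at every control incidence.

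**3. Inputs.** The study size comes from V.G: 134 evaluable, 168 enrolled. These figures are for fusion; no size or power is stated for the AE test. The 134 reproduces with a one-sample normal approximation (null 0.806, alternative 0.706, two-sided 0.05, 80% power):

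n = (1.96·√(0.806·0.194) + 0.8416·√(0.706·0.294))² / 0.10² = (0.7750 + 0.3834)² / 0.01 = 134.2

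and 134 / 0.80 = 167.5, rounded up to 168. The documents do not give the size of the IDE study or its AE incidences. I assume n_d = 100, 250 or 400, and control incidences of 1%, 5%, 20% or 30%.

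**4. Worked cases** (n_e = 134, n_d = 250). The interval is d ± 1.96·√(p_e(1−p_e)/n_e + p_d(1−p_d)/n_d).

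- Observed 50% against 20%: d = +30 points, SE = √(0.25/134 + 0.16/250) = 5.0 points, CI +20.2 to +39.8. The lower limit is above −10, so it **passes as written**. The upper limit is above +10, so it fails when mirrored.
- Observed 5% against 20%: d = −15 points, SE = √(0.0475/134 + 0.16/250) = 3.15 points, CI −21.2 to −8.8. The lower limit is below −10, so it **fails as written**. The upper limit is below +10, so it passes when mirrored.

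**5. Pass probabilities.** These come from exact enumeration of the two binomials with the same interval. The ranges cover n_e = 134 and 168 and n_d = 100, 250 and 400. "Mirrored" in the table means upper limit < +10%.

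| Control p_d | Device p_e | As written | Mirrored |
|---|---|---|---|
| 20% | 40% | 99.9–100% | about 0% |
| 5% | 25% | 100% | 0% |
| 20% | 30% | 94–99.9% | 2.2–3.0% |
| 20% | 20% | 48–79% | 48–77% |
| 20% | 16% | 23–41% | 80–97% |
| 20% | 10% | 2–3% | 99–100% |
| 20% | 5% | 0–0.2% | 100% |
| 30% | 15% | 0–0.3% | 99.6–100% |
| 5% | 1% | 68–99% | 100% |
| 1% | 6% | 100% | 62–72% |

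As written, the chance of passing rises with the device's AE incidence. At 20% control it goes from near zero when the device is much safer to near certainty when the incidence has doubled.

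**The case against.** The best defence is that the IDE test does not decide alone. The literature comparison is aimed the right way and both must be met, so an excess that slips through the first could be caught by the second. AEs are also adjudicated independently and tabulated against each article, so a large excess would be visible. This stands in part: the error lies in the IDE comparison, and the plan as a whole is not blind. But the literature check has no margin and no exact decision rule, reaches only events the articles report, and rests on data that V.C considers inadequate alone. It also cannot help a safer device that fails the IDE test.

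Second, the penalty on a safer device is not universal. At 5% control, a device at 1% still passes 68–99% of the time, and at 20% control a device at 16% passes 23–41%. That is right: near-certain failure needs a reduction of roughly 10 to 15 points from a control incidence of 20% or more. The failure to limit harm has no such condition.

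Third, the control incidences and IDE sample size are assumptions. They affect the exact percentages but not the direction.

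Fourth, mirroring the rule does not make every category well tested. A flat 10-point margin still passes a rise from 1% to 6% in 62–72% of trials, and at equal 20% incidence the mirrored test passes only 48–77%. Both are true, but they concern the margin and the power and do not defend the present direction.

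**Conclusion.** The concern holds and must be fixed. The IDE comparison in V.C tests whether the device is not much safer, when it should test whether the device is not much more harmful. That follows from the definitions and hypotheses alone and needs no assumed figure. The size of the effect does rest on assumptions (IDE size 100 to 400, control incidence 20% to 30%, Wald 95% interval, 134 or 168 study patients). Under them, a true excess of 20 points or more passes with probability at least 0.997, and a true reduction of 15 points or more passes with probability at most 0.003. For control incidences below 10%, the stated null hypothesis is impossible. The fusion test in V.G is correctly directed and is not affected.

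**What to change.** In V.C, for AE incidence, replace the hypotheses with H0: p_e − p_d ≥ +0.10 against H1: p_e − p_d < +0.10. Infer non-inferiority when the upper limit of the 95% confidence interval for p_e − p_d is below +10%. An equivalent route for incidence is to define p as the proportion free of the event and keep the present lower-limit rule.

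The combined criterion should refer to the corrected rule. The literature comparison needs no change of direction. Two gaps should be closed in the same edit: give that comparison an explicit decision rule, and state the unit in which a 10% margin applies to event rates as distinct from incidences.

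The direction change costs SAP wording and one line of code. It needs no extra data or patients, and the sample size of 134/168 is unaffected because it was set on fusion. The sponsor should note the limits on power and on the flat margin for rare events described above.

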Removal and Refusion				

E. Baseline and Operative Analysis

Baseline summaries will be chosen to be appropriate for the scale and distribution of the measures being analyzed. Statistical methods will be the same as described above for the non primary endpoint analyses.

F. Missing data

Except for the primary analysis, if a value, at any assessment is not available for analysis, it will be excluded from summaries.

G. Study Hypothesis and Sample Size Determination using a Literature Control

Study Hypothesis

The hypothesis is Dynesys fusion rate is non-inferior to the historical literature sample data estimated fusion rate of 80.6%. This hypothesis will be assessed by testing that the difference between the experimental rate (p_e) and the historical control rate (p_c) is not worse than 10%. The non-inferiority test will be inferred if the lower limit of the 95% confidence interval around the **treatment difference** between 2 groups is greater than $\delta = -10\%$.

$$H_0: p_e - p_c \leq -0.10$$

$$H_1: p_e - p_c > -0.10$$

Sample Size

Sample size for the Dynesys Post-Market Surveillance Study was estimated using SAS, Proc Power with a testing level alpha (Type I) error level of 0.05, 80 percent statistical power, a meaningful difference of 10%, and a success rate for lumbar fusion from the literature historical

control group of 80.6% (0.806). For this set of criteria, the sample size was 134, without adjustment for attrition. With a 20% attrition sample added, this would result in a sample size of 168.

Sample size estimates are presented in Table 2.

Table 2: Proposed Sample Sizes

Primary Endpoint	Difference	Predicted Success	Type I Error	Power	N Patients
Radiographic Success (Fusion)	10%	80.6%	0.05	80%	168

VI. TIMELINE

A. Clinical Trial Agreement

No portion of this protocol will be implemented until both copies of the Clinical Trial Agreement have been completed by both parties.

Table 3: Study Timeline

Study Timeline	Sponsor Expectation
Expected date of Study Initiation	March 2012
Expected date of first IRB Approval(s)	January 2012
Expected monthly number of sites obtaining IRB approval	1
Expected subject enrollment initiation	March 2012
Expected average number of subjects to be enrolled/month	7
Expected Date of Subject Enrollment Completion	March 2014
Expected date of Subject follow-up Completion	March 2016
Reports	
Interim Postmarket Surveillance Study Report	Every 6 months through 2 years, annually thereafter

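### The article-by-article adverse-event comparison is called non-inferiority but has no margin and no deciding limit, so no reading of it tests non-inferiority

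*Combined protocol and SAP*

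**What the plan says.** Section V.C (Primary Analysis: Safety Endpoints and Evaluation) sets two AE comparisons.

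- **Against the earlier Dynesys IDE study.** The 95% interval for the difference p_e - p_d must have a lower limit above -10%, where "p_d is the incidence or rate in the historical study group".
- **Against the literature.** For each AE category the plan states: "a non-inferiority analysis will be performed assessing how the incidence and rates in the experimental group compare to the AEs as described in each" (meaning every article behind the meta-analysis). The method is given in two sentences. First, "The incident rate that occurs in the experimental data will be computed with a 95% confidence interval". Then "Any AEs that occurred in any of the literature control studies will be compared to those ranges", with the aim "to ensure that the incidence or rate found in the experimental group does not exceed the incidence or rate in the literature data".

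The two are joined in one rule: "Non-inferiority will be inferred if the assessment of AEs under both analyses meets the specified criteria for non-inferiority".

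The section explains why the IDE study was added: "Assessing adverse events (AEs) using only the literature control data is not sufficient, because of the heterogeneity of reporting across the manuscripts". Section V.D separately plans a descriptive table of AE incidence, article by article, beside the trial result.

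**The concern.** A non-inferiority test needs a margin, an interval for the difference between the groups, and a statement of which limit decides. The literature comparison has none of these. Its only interval is the trial's own, and each article's rate is treated as a known constant. The -10% margin cannot be borrowed. It is tied to the IDE group and to an interval for a difference, which the literature comparison never computes. The joint rule therefore refers to specified criteria, but none is specified for this half.

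The comparison sits under a primary safety heading and is required for the overall AE conclusion. It is repeated for every AE category and every contributing article, with no rule for articles that disagree. Depending on how the sentence is read after the data are in, the same results could be reported as non-inferior or not.

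**Working it through.** **Inputs**

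- Section V.G: 134 subjects before attrition is added, 168 enrolled. The plan's 134 reproduces as [1.960 × √(0.806 × 0.194) + 0.842 × √(0.706 × 0.294)]² / 0.10² = 134.2, and 134 / 0.8 = 167.5, i.e. 168. This is the fusion sample size. The plan gives no figure for the AE comparison.
- Both n are used, because Section V.A does not restrict the analysis population to completers.
- Literature AE rates: not given (the Section V.D table is an empty shell). **Assumption:** article rate r from 1% to 20%.
- Interval method: not named. **Assumption:** exact (Clopper-Pearson), with Wald as a check.

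**Formulas.** For x events in n, the lower limit L(x) is the 2.5% quantile of Beta(x, n-x+1), and the upper limit U(x) is the 97.5% quantile of Beta(x+1, n-x). The pass probability is the binomial(n, p) probability of all x that satisfy the rule, where p is the true trial rate. Each result is for one AE category against one article.

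**Reading 1: pass if L(x) ≤ r.** At n = 134 and r = 2%, L(6) = 1.66% and L(7) = 2.13%, so up to 6 events pass (4.5% observed, 2.2 times the article rate). P(X ≤ 6 | p = 4%) = 0.71. At r = 5%, L(12) = 4.71% and L(13) = 5.27%, so P(X ≤ 12 | p = 10%) = 0.41.

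Probability that a doubled true rate passes:

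| Article rate | 1% | 2% | 3% | 5% | 10% | 15% |
|---|---|---|---|---|---|---|
| n = 134 | 87% | 71% | 59% | 41% | 12% | 2% |
| n = 168 | 88% | 64% | 57% | 28.5% | 6% | 0.5% |

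With Wald intervals at n = 134 the figures are 91% at 2%, 53% at 5% and 12% at 10%. This reading also rewards imprecision: for 5% against a true 10%, the pass rate is 79% at n = 40, 41% at n = 134 and 10% at n = 300.

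**Reading 2: pass only if U(x) ≤ r.** At n = 134, U(0) = 2.72%, so at r = 1% or 2% even zero events fail. At r = 5%, U(1) = 4.09% and U(2) = 5.29%, so at most 1 event passes, and P(X ≤ 1 | p = 5%) = 0.008. Over r = 1% to 20%, an equal true rate passes 0% to 1.8% of the time at n = 134 and at most 2.3% at n = 168. With Wald it is at most 9.3% (n = 134, r = 2% to 15%).

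**Reading 3: pass if x/n ≤ r.** An equal true rate passes 48% to 63% of the time.

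**Article sampling error.** The groups in the Section V.A demographic table, drawn from the same literature, run from 21 to 182 patients. One event in 21 is 4.8%, with exact interval 0.1% to 23.8%. Nine in 182 is 4.9%, with interval 2.3% to 9.2%. The rule treats both as the same fixed benchmark.

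**The case against.** Four points on the other side deserve weight.

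- **A reader might infer that the rule lets a doubled AE rate through in general.** The table does not support that. At an article rate of 5% a doubled rate fails more often than it passes, and at 10% or more it is usually caught. The documents give no literature rates to place the trial on this scale.
- **A reader might infer that the overall safety claim is either far too easy or nearly impossible.** That does not follow. The pass rates are for one category against one article, and both AE analyses must succeed. If every category must pass, and five independent categories all had doubled rates (an assumption), Reading 1 at n = 134 would pass all five with probability 0.71⁵ = 18% at 2%, 0.587⁵ = 7% at 3% and 0.412⁵ = 1% at 5%. The point-estimate reading is neither extreme.
- **A reader might infer that the plan contradicts itself by using literature it finds too heterogeneous.** It says only that the literature alone is not sufficient, and then adds a second source. Using both is consistent with that.
- **Deleting the literature comparison removes the only AE criterion aimed at excess harm.** This stands. The IDE test requires a lower limit above -10%. Where a higher rate is worse, that excludes only a rate more than 10 points lower. The fix must deal with it.

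None of this supplies the missing margin or deciding limit.

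**Conclusion.** The concern holds for the rule itself. Reading 1 takes the absence of a significant excess as non-inferiority, Reading 2 is a superiority test, and Reading 3 makes no allowance for chance. That conclusion does not depend on the assumed rates.

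The size does depend on them. Under Reading 1 the weakness is mainly for uncommon AEs: with exact intervals a doubled rate is more likely than not to pass up to an article rate of about 3%, at either n. Under Reading 2 an equal rate fails almost always across the whole range tried. All of these figures rest on assumed article rates, one category against one article, and 134 or 168 subjects. The chance that the complete safety rule passes cannot be computed from the documents. The plan should be changed, and wording is enough to do it.

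**What to change.** 1. Remove the article-by-article comparison from the rule that joins the two analyses. Keep it as the descriptive table already planned in Section V.D, with each article's incidence and exact 95% interval beside the trial's.
2. At the same time, restate the IDE-study AE test in the harm direction: the upper 95% limit of p_e - p_d must lie below a stated positive margin. Otherwise the only criterion left would not exclude a higher AE rate.
3. If a literature-based inferential claim is kept, test the upper 95% limit of the trial-minus-literature difference against a stated margin. The literature's standard error, including between-study variation, must be in the interval.

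The margin needs thought. As an illustration (Newcombe interval, n = 134, one article of 21 to 182 patients), a 10-point margin at a literature rate of 5% passes an equal rate 80% to 94% of the time and a doubled rate 26% to 32%. At 3% it still passes a doubled rate 57% to 70% of the time, so 10 points is wide for rare AEs. A 5-point margin at 5% passes an equal rate only 29% to 46% of the time.

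The cost is SAP wording and one fewer inferential claim. No data collection changes.

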Patients who complete the Pre-Operative visit, but do not receive treatment with the study device will be considered discontinued. The Patient Discontinuation case report form will indicate proposed surgery not performed.

Patients have a right to withdraw permission (revoke informed consent authorization). Patients who withdraw consent will have no further private health information collected. Once authorization is revoked, patients may no longer participate in the research activities, but standard medical care will not be affected. Revoking authorization only affects information obtained after the request has been received, but not information obtained prior to that time. Patient withdrawal will be documented on the Patient Discontinuation case report form.

Remuneration will be provided to all subjects who complete scheduled follow-up office assessments at 24 months and annual follow-up visits thereafter as required. The subjects' financial compensation package will be outlined in the Informed Consent Form and approved by the Institutional Review Board (IRB) prior to the start of the study.

Every attempt will be made to contact patients who are non-compliant or lost to follow-up. Three contact attempts by certified letters will be documented. Patients who are lost to follow-up will be documented on the Patient Discontinuation case report form.

To compensate for a potential 20% attrition rate, additional subjects have been added to the sample size. The number of enrolled and completed subjects will be closely monitored, and if needed patients will be added to assure the study endpoints can be achieved.

K. Data Collection

The purpose of the case report form is to reconstruct the study. Information should always be documented in the source document first, and then transferred to the case report form, either paper or electronic. As an exception, the Oswestry Disability Index (ODI) and Patient Assessment forms are considered source documents. It is recommended that patient questionnaires be completed prior to the patient meeting with any clinical staff to minimize the bias in the study or in accordance with site specific standard operating procedures.

Patient confidentiality will be protected at all times and patient identifiers will be used.

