To assure that baseline characteristics of the history control data are similar to those found in the experimental data, the demographic characteristics from the study data will be reviewed to confirm that the characteristics of age, gender, smoking status, and preoperative diagnosis in the test data are similar to the data that existed for the historical control data. The rate of males and rate of smokers will be checked against the 95% confidence interval found in the point estimate table. The distribution of preoperative diagnoses will be tested for no difference between the historical control and the test group. The average age will be checked to assure that it is in the range from 41 to 75. If any differences are noted, patients with extreme data will be removed until the rates and means of the test population do reside within the bounds determined by the meta-analysis. If needed, more patients will be enrolled in the test group to assure that the sample size is sufficient for inferential testing.

B. Primary Analysis: Fusion Status

Fusion success will be defined as evidence of bridging bone and angulation of <5° and translation of <3mm at treated levels at 24 months. Radiographic assessment will determine for each patient a fusion status, either fused or not fused. The primary endpoint is fusion status at Month 24. Efficacy will be confirmed by the achievement of fusion in the experimental group when compared to the rate established in a literature control. Normand (1999) provided the direction for the meta-analysis¹. The details of that analysis included creating population mean and variance estimates using a weight of the inverse of the variance. (See pp. 335-336 for complete description of the algorithm) A point estimate of 80.6% with a standard error of 2.6% was established. The 95% confidence interval for this point estimate is (75.0%, 86.3%).

If Month 24 fusion status cannot be determined, but fusion was determined to have occurred earlier, the Month 24 status will be considered fused. Otherwise, subjects without earlier fusion who are missing Month 24 values will be excluded from primary analysis.

For the purpose of a sensitivity analyses, all subjects excluded as described above for a missing Month 24 fusion status will be defined as not fused.

C. Primary Analysis: Safety Endpoints and Evaluation

Subjects will be clinically evaluated for adverse experiences and functional outcomes over the course of 24 months.

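### The sample size of 134 (168 enrolled) omits the literature rate's 2.6% standard error; under the planned 95% CI rule, power is about 64%, not 80%

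*Combined protocol and SAP*

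**What the plan says.** - **Endpoint and benchmark (V.B).** "The primary endpoint is fusion status at Month 24". The comparator is a meta-analysis of published series: "A point estimate of 80.6% with a standard error of 2.6% was established". A 95% interval of 75.0% to 86.3% is also given.
- **Decision rule (V.G, Study Hypothesis).** The hypothesis is assessed by "testing that the difference between the experimental rate (p_e) and the historical control rate (p_c) is not worse than 10" per cent. "The non-inferiority test will be inferred if the lower limit of the 95% confidence interval around the" treatment difference between the two groups is above -10%. The null hypothesis is p_e - p_c ≤ -0.10.
- **Sizing (V.G, Sample Size, and Table 2).** The inputs listed are alpha 0.05 (sidedness not given), power 80%, a 10% difference and a rate of 0.806. "For this set of criteria, the sample size was 134, without adjustment for attrition". Adding 20% for attrition gives 168.
- **Adding patients.** IV.J says that "if needed patients will be added to assure the study endpoints can be achieved". V.A says that, if needed, "more patients will be enrolled in the test group to assure that the sample size is sufficient for inferential testing".

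**The concern.** The rule rests on a confidence interval for a difference between two rates, and the plan itself says one of them is estimated with error. That error belongs in the interval, but it is not among the sizing inputs. The 80% in Table 2 therefore describes a comparison with a known constant, not the comparison that V.G sets out.

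This is the primary endpoint. At 64% power, a device that fuses exactly as often as the literature would miss non-inferiority about 36% of the time, while readers of the plan would expect 20%. The provisions for adding patients do not settle the matter: the only target the plan gives for judging whether the sample is sufficient is 134 evaluable, and that number is too small for 80% under the stated rule.

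**Working it through.** **Inputs.** p_c = 0.806 and literature SE = 0.026 (V.B). Margin 0.10, 95% CI rule, alpha 0.05, power 80%, n = 134 evaluable and 168 enrolled (V.G). The true Dynesys rate is taken as 0.806, the rate used in the sizing.

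**1. Reproducing 134.** Two standard calculations fit, and both hold 80.6% fixed.
- Two-sided one-sample test, null 0.806, alternative 0.706: n = [1.96·√(0.806·0.194) + 0.8416·√(0.706·0.294)]² / 0.10² = 134.2.
- Equivalence within ±10 points at 0.05: n = 0.806·0.194·[(1.645 + 1.282)/0.10]² ≈ 133.9.

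Neither is the planned non-inferiority test. One-sample non-inferiority formulas (null 0.706, alternative 0.806) give 150.2 or 122.7 at two-sided 0.05, and 117.1 or 96.7 at one-sided 0.05. The documents do not show which test was run, and the results below do not depend on it. The attrition step is correct: 134/0.8 = 167.5, so 168.

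**2. Standard error of the difference at n = 134.**
- Study arm: 0.806·0.194/134 = 0.001167, an SE of 3.42 points.
- Literature: 0.026² = 0.000676.
- Combined: √(0.001167 + 0.000676) = 4.29 points. The literature term is 37% of the variance.

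**3. Power = Φ(0.10/SE − 1.96).**
- n = 134: Φ(0.10/0.0429 − 1.96) = Φ(0.369) = 64.4%.
- n = 168: SE = 4.01 points, Φ(0.535) = 70.4%.
- With binomial outcomes in the study arm and normal error in the literature estimate: 64.0% and about 70%.
- With the literature estimate held at its observed 80.6%: the pass mark is 107/134 fused, and exact power is 63.6% (71.9% at 168).
- Rounding of the SE (2.55% to 2.65%) moves the result at 134 only from 65.0% to 63.8%.

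**4. Evaluable patients needed for 80%.**
- 95% CI: 0.1564/[(0.10/2.8016)² − 0.026²] = 261.4, so 262.
- 90% CI: 0.1564/[(0.10/2.4865)² − 0.026²] = 166.1, so 167.

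**5. Dependence on the true rate (formula, n = 134).**

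| True rate | Power |
|---|---|
| 80.0% | 58% |
| 80.6% | 64% |
| 82.0% | 77% |
| 83.0% | 85% |

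With binomial outcomes the last two are 76% and 83%. By formula, 80% power at 134 needs a true rate of about 82.4%.

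**6. If 80.6% is treated as exact (n = 134).** Power is 71% (exact binomial, pass mark 106), 75% (score approximation), 78% (Wald or score enumerated, pass mark 105) or 83% (Wald approximation).

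**7. One-sided type I error at a true difference of -10 points (nominal 2.5%).** With the literature error left out of the interval: 6.1% (Wald) or 4.6% (score). With it included: 3.0% (Wald).

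**The case against.** **The plan never writes out the interval, so 80.6% could be a fixed performance goal.** That reading matches the sizing inputs, and V.G does not state the variance. But the plan nowhere declares a performance goal. It specifies a difference between two groups, calls the rate estimated, and reports its standard error. Even on the fixed reading, power at 134 is 71% to 83% depending on the method, and the benchmark's error goes uncounted. The part that stands is that the text is under-specified and has to say which is meant.

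**134 is correct for its inputs.** True, and so is the step to 168. The fault is that those inputs do not describe the planned comparison.

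**The missing-data rule changes the pass probability.** V.B counts a patient with undetermined Month 24 status as fused if fusion was seen earlier. Assume 168 enrolled, 34 missing at Month 24 and 80.6% fused among completers. If 0%, 10%, 25% or 40% of the missing had fused earlier, the simulated pass probability is 64%, 69%, 76% or 81%. This shows that 64% is not a forecast of the trial's result. The rise comes from adding patients who can only be successes, so it does not rescue the design or alter power at a given evaluable number.

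**The meta-analysis is finished, so power given its observed value may be the relevant figure.** A normal approximation then gives 67.9% at 134 and 75.9% at 168. The exact values are 63.6% and 71.9%. Discreteness matters here: the exact figure at 135 is 69.8%. None of the figures at 134 or 135 reaches 80%.

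**Alpha 0.05 might be one-sided.** V.G fixes a 95% interval. A 90% interval would still give only 75.3% at 134.

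**Conclusion.** The concern holds. Under V.G's 95% interval, with the 2.6% standard error that V.B reports, power is about 64% at 134 evaluable patients and about 70% if none of the 168 is lost. The planned case is 134, so 64% is the figure to set against Table 2's 80%.

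The result assumes a true rate of 80.6% and an interval that includes the literature error. The first assumption is the sizing's own. The second is the natural reading of V.G, though the plan does not spell it out. Holding 80.6% fixed instead would raise nominal power but exchange the shortfall for excess type I error.

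**What to change.** In V.G and Table 2:

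1. State that the 95% confidence interval for p_e - p_c includes the literature standard error of 2.6%, and give the variance formula.
2. State the Proc Power test, null, alternative and sidedness that produced 134.
3. Restate power for this rule as about 64% at 134 evaluable and about 70% at 168, assuming a true rate of 80.6%.

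The cost is protocol and SAP wording. The one downside is a less favourable stated power. No additional enrolment is asked for; the figure of 262 shows the size of the gap and is not a proposed target.
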